#### 6.3.7.1.2 Severity Definition

ARIA-E severity is based on radiographic severity as captured on BMWs.

Protocol No. AL002-2 Last Revision Date: 12 Aug 2025

## 6.3.7.1.3 Resolution and Time to Resolution Definition

- ARIA-E is considered resolved for a participant if all the subsequent MRI scans showed no ARIA-E following the last MRI scan showing ARIA-E.
- Time to resolution is defined as the number of days from the exam date of the first MRI scan showing ARIA-E to the exam date of the earliest MRI showing no ARIA-E after the last one showing ARIA-E. If a participant had a resolved but recurrent ARIA-E after the previous one was resolved, both times to resolution are included.

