Participants in Part 1 with MRI evidence of ARIA at the Day 15 or Day 43 MRI will be discontinued from study drug administration. Participants in Part 1 with ARIA after Day 43 and participants in Part 2 with MRI evidence of ARIA at any visit will be managed according to the guidelines in Table 7.

AL002 Alector, Inc.

Table 7: Dosing Guidelines for ARIA

Finding	Asymptomatic/Symptomatic	Action	
Milda ARIA-E	Asymptomatic or Symptomatic	Suspend dosing until resolution of ARIA-E or	
Moderate ^b ARIA-E	Asymptomatic or Symptomatic	stabilization of ARIA-H. After resolution (ARIA-E) and/or stabilization (ARIA-H), if	
Severe ARIA-E	Asymptomatic or Symptomatic	participant dosing is restarted, they must receive the same dose they received immediately prior	
Mild or Moderate ARIA-H	Asymptomatic	to the ARIA-E/ARIA-H findings and continue on that dose for the remainder of the study. After resuming dosing, 5-10 days before their second post-resumption dose, participants must undergo an unscheduled MRI that must be assessed by the Central Reader for ARIA-E/H before the next dose is administered.	
		For mild or moderate symptomatic ARIA-E the use of oral or IV steroids can be considered.	
		For severe symptomatic ARIA-E it is recommended to hospitalize the participant for close observation and consider the use of IV steroids such as high-dose dexamethasone or a similar agent.	
Mild or Moderate ARIA-H	Symptomatic	Permanently discontinue treatment	
Severe ARIA-H	Asymptomatic or Symptomatic	Permanently discontinue treatment	
Serious ^c ARIA-E or Serious ARIA-H	Symptomatic	Permanently discontinue treatment	
Serious ^c ARIA-E or Serious ARIA-H	Asymptomatic	Suspend dosing until resolution of ARIA-E or stabilization of ARIA-H. After resolution (ARIA-E) and/or stabilization (ARIA-H), if participant dosing is restarted, they must receive the same dose they received immediately prior to the ARIA-E/ARIA-H findings and continue on that dose for the remainder of the study. After resuming dosing, 5-10 days before their second post-resumption dose, participants must undergo an unscheduled MRI that must be assessed by the Central Reader for ARIA-E/H before the next dose is administered.	
A second occurrence of ARIA-E after full resolution of a prior occurrence of ARIA-E	Asymptomatic or Symptomatic	Permanently discontinue treatment	

ARIA-E=amyloid-related imaging abnormality-edema; ARIA-H=amyloid-related imaging abnormality-hemosiderin deposits; MRI=magnetic resonance imaging.

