## 6.3.7.1.4 Time to First Occurrence and Recurrence Definition

- Time to the first occurrence is defined as the number of days from the first dose date to the exam date of the first MRI scan showing ARIA-E.
- For a participant, if there was an MRI scan showing ARIA-E, followed by a subsequent MRI scan not showing ARIA-E, followed by a subsequent MRI scan again showing ARIA-E, this participant is considered to have a reoccurrence of ARIA-E.

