APOE genotype, time to the first occurrence, resolution, time to resolution, and reoccurrence will be summarized for participants with ARIA-E. APOE genotype and time to the first occurrence will be summarized for participants with post-baseline new ARIA-H.

The number and percentage of participants who had a post-baseline ARIA-E but did not have a new ARIA-H any time post-baseline will be summarized. The number and percentage of participants who had a new ARIA-H but did not have an ARIA-E any time post-baseline will be summarized. Similarly, the number and percentage of participants who had a new ARIA-H and an ARIA-E any time post-baseline will be summarized.

All the MRI summaries described above will also be provided separately for participants with the following APOE genotype(s) (1) e4/e4, (2) e4 carriers (including e2/e4, e3/e4 and e4/e4), (3) non-e4 carriers (excluding e2/e4, e3/e4 and e4/e4), and (4) e4 heterozygous carriers (including e2/e4 and e3/e4).

The Kaplan-Meier curve for the time to the first occurrence of ARIA-E will be plotted. For participants experienced at least one ARIA-E, the time to the first occurrence of ARIA-E is the time from the first dose date to the onset date of the first ARIA-E occurrence. For participants who did not experience ARIA-E, the censor date will be the earlier date of the last MRI scan date and the last dose date plus 90 days. Similarly, the Kaplan-Meier curve for the time to the first occurrence of new ARIA-H will be plotted.

All MRI findings will be listed.

Protocol No. AL002-2 Last Revision Date: 12 Aug 2025

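### The SAP's ARIA-E resolution rule cannot classify anyone as unresolved, and its time-to-resolution formula conflicts with its own sentence on recurrent cases

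*SAP*

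**What the plan says.** SAP 6.3.7.1.1 makes each MRI scan showing vasogenic edema an event. No episode is defined anywhere in SAP 6.3.7.1.

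SAP 6.3.7.1.3 then has two bullets.
- Resolution: "ARIA-E is considered resolved for a participant if all the subsequent MRI scans showed no ARIA-E following the last MRI scan showing ARIA-E".
- For the time to resolution: the days "from the exam date of the first MRI scan showing ARIA-E to the exam date of the earliest MRI showing no ARIA-E", where the end scan is the "earliest MRI showing no ARIA-E after the last one showing ARIA-E". The same bullet adds: "If a participant had a resolved but recurrent ARIA-E after the previous one was resolved, both times to resolution are included".

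SAP 6.3.7.1.4 covers recurrence. After a positive, a clear and another positive scan, "this participant is considered to have a reoccurrence of ARIA-E".

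SAP 7.5.7 uses these definitions: "time to the first occurrence, resolution, time to resolution, and reoccurrence will be summarized for participants with ARIA-E". That section gives a Kaplan-Meier curve and a censoring date for time to first ARIA-E. It gives neither for time to resolution.

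The protocol treats resolution as something seen on a follow-up scan (7.11), asks for unscheduled scans every 4 to 6 weeks until ARIA-E has resolved (7.11.1.2), and treats occurrences as separate. Table 7 has its own row for "A second occurrence of ARIA-E after full resolution of a prior occurrence of ARIA-E".

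**The concern.** The resolution rule looks at scans after the last positive scan and asks whether they are all negative. They must be, or the positive scan would not have been the last. The rule does not require that a later scan exists, so a participant last seen with ARIA-E passes it.

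The two bullets then disagree about that participant, who is resolved under the first and has no end date under the second. The number resolved and the number with a resolution time would differ, and nothing explains the gap.

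The formula's first and last scans are those of the participant, not of an episode. That conflicts with the sentence keeping both times for a recurrent case. It also leaves unstated how the second time is calculated and what happens when a second episode is still open.

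At stake are the resolved proportion and the duration of an adverse event of special interest that the protocol lists among the identified risks (1.3, 7.2). Open cases are plausible. Protocol Table 9 schedules the last MRI at Week 97 and none at the follow-up or early termination visits, and participants entering the extension study need no follow-up visits. Withdrawal or rollover can therefore end the 4-to-6-week scans within this study's data before clearance.

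**Working it through.** The plan gives no figure to reproduce, so the check applies the two bullets exactly as worded.

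**Step 1: can the resolution rule fail?** Take every positive/clear sequence of 1 to 8 scans with at least one positive.
- Sequences: sum over L = 1 to 8 of (2^L − 1) = 510 − 8 = 502.
- Sequences ending on a positive scan: sum over L = 1 to 8 of 2^(L−1) = 255.
- Sequences the rule calls not resolved: 0 of 502.
- With at least one later clear scan required: 255 of 502 become not resolved.

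These are counts of possible patterns, not forecasts of how often each occurs.

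**Step 2: what does the time formula return?** Assumed scan dates are Day 22 (first positive), Day 57, Day 160 and Day 195. They fit the protocol schedule: the MRI 5 to 10 days before Dose 2 (Day 29) falls on Days 19 to 24, the one before the Week 25 dose (Day 169) falls on Days 159 to 164, and 35 days lies within 4 to 6 weeks. Further clear scans between Days 57 and 160 would change nothing below.

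| Scans | Resolution rule | Formula sentence alone | Per episode |
|---|---|---|---|
| Positive 22, clear 57 | Resolved | 57 − 22 = 35 | 35 |
| Positive 22, positive 57, none later | Resolved | No end date | Unresolved at Day 57 |
| Positive 22, clear 57, positive 160, clear 195 | Resolved | 195 − 22 = 173 | 35 and 195 − 160 = 35 |
| Positive 22, clear 57, positive 160, none later | Resolved | No end date | 35, then unresolved at Day 160 |

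In the third row the clear interval is 160 − 57 = 103 days, and 35 + 103 + 35 = 173.

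**Step 3: range.** Let the first positive scan p1 be Day 19 to 24, the recurrence p2 Day 159 to 164, and clearance a = 28 to 42 days after each.
- Formula: p2 + a − p1, from 159 + 28 − 24 = 163 to 164 + 42 − 19 = 187 days.
- Clear interval within it: p2 − (p1 + a), from 159 − (24 + 42) = 93 to 164 − (19 + 28) = 117 days.
- Per episode: 28 to 42 days.

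**Step 4: who contributes a time?** The formula needs a clear scan after the last positive one. Rows 2 and 4 therefore contribute nothing under it, although row 4 contains a completed first episode. The summary covers only participants seen to clear, which tends to shorten apparent duration.

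**The case against.** Three defences deserve weight.

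First, a reader might infer from the formula that the SAP counts the ARIA-free interval as ARIA-E. The documents do not support that. The sentence keeping both times shows that one time per occurrence is intended, and applied that way the gap drops out. The 173 days is one reading of a formula at odds with its neighbour, not what the SAP plainly instructs. What stands is the conflict itself, because no text says how each of the two times is calculated.

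Second, the resolution rule can be said to presuppose later scans, since the time formula needs a clear scan and the protocol describes resolution as a follow-up finding. A sensible programmer might add that condition. So it would go too far to say that the published table will show 100% resolved, or that the time formula itself counts unresolved cases as resolved. But the condition is not written, and the rule as written gives a wrong answer for a final positive scan.

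Third, a reader might infer an effect on dosing or on dose selection. Dosing follows the central reader's worksheets and protocol Table 7, not this summary. No text ties resolution time to dose choice, and ARIA-E and ARIA-H are named as identified risks without ranking. The listings of MRI findings and events of special interest, and the recorded adverse event outcomes, would also help to expose an error. These points limit the consequence. They do not make the definition right.

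**Conclusion.** The concern holds for the definitions. The resolution rule is true by construction, and the formula's participant-level wording conflicts with the recurrence sentence. Unresolved cases contribute no time and have no censoring rule.

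The logical result (0 of 502 patterns failing) needs no assumption beyond reading the rule as written. The 173 days against 35 and 35, and the range of 163 to 187 days, rest on assumed scan dates. The documents give no ARIA-E rates, recurrence rates or durations, so the number of participants affected cannot be stated.

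The outputs are descriptive safety summaries. The primary efficacy analysis and type I error are untouched.

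**What to change.** Reword SAP 6.3.7.1.3 by episode:
- An episode starts at the first post-baseline MRI showing ARIA-E, or at the first MRI showing it after a clear MRI.
- It resolves at the first later MRI without ARIA-E. At least one such scan is required; every other episode is reported as unresolved at last MRI.
- Time to resolution is the interval from the start scan to the resolving scan, calculated separately for each episode.
- In SAP 7.5.7, report resolved out of total episodes. Estimate time to resolution of the first episode by Kaplan-Meier, censoring unresolved cases at the last MRI.

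Separate rows for first and recurrent episodes would help, but they are a matter of presentation. The recurrence definition in 6.3.7.1.4 can stay as it is.

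The cost is a few lines of SAP text and minor programming on MRI data already collected. Protocol Table 7 needs no change.

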## 6.3.7.1.4 Time to First Occurrence and Recurrence Definition

- Time to the first occurrence is defined as the number of days from the first dose date to the exam date of the first MRI scan showing ARIA-E.
- For a participant, if there was an MRI scan showing ARIA-E, followed by a subsequent MRI scan not showing ARIA-E, followed by a subsequent MRI scan again showing ARIA-E, this participant is considered to have a reoccurrence of ARIA-E.

#### 6.3.7.2 New ARIA-H

#### 6.3.7.2.1 Event Definition

A new event of ARIA-H is defined as an MRI scan at a post-baseline visit if any of the criteria below as captured on its BMW is satisfied:

- CFB in the number of microhemorrhages > 0, or
- CFB in the number of areas of leptomeningeal hemosiderosis (also referred to as superficial siderosis) > 0, or
- Presence of macrohemorrhages.

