- 9. Participant has any of the following eye conditions: a history or presence of uveitis, a serious chronic inflammatory condition of the eye, a current eye infection, or any ongoing eye disorder requiring anticipated invasive eye procedures or injectable medical therapy (eg, ranibizumab or aflibercept for macular degeneration or diabetic eye disease) during the study period.
- 10. Participant has any history of schizophrenia, schizoaffective disorder, major depression, or bipolar disorder.
 - a. A history of major depression is acceptable if no episode has been reported within the previous 2 years. Treatment with antidepressant medications is allowed.
- 11. Participant is at risk of suicide in the Investigator's opinion.

Alector, Inc.

- 12. Participant has history of alcohol and/or moderate to severe substance use disorder (according to the Diagnostic and Statistical Manual of Mental Disorders, 5th Edition) within the past 2 years.
 - a. Nicotine use is allowed.

Imaging-related exclusion criteria:

- 13. Participant has MRI evidence of
 - a. >2 lacunar infarcts.
 - b. Any territorial infarct > 1 cm³.
 - c. White matter hyperintense lesions on the FLAIR sequence that correspond to an overall Fazekas score of 3.
- 14. Participant has presence on MRI of >5 microbleeds and/or >1 area of leptomeningeal hemosiderosis based on central read.
- 15. Participant has presence of significant cerebral vascular pathology as assessed by the MRI Central Reader.
- 16. Participant is unable to tolerate MRI procedures (eg, due to anxiety or claustrophobia) or has contraindication to MRI, including but not limited to, the presence of pacemakers that are not MRI compatible, aneurysm clips, artificial heart valves, ear implants, or foreign metal objects in the eyes, skin, or body that would contraindicate an MRI scan; or any other clinical history or examination finding that would pose a potential hazard in combination with MRI. Those who are able to tolerate MRI with intermittent use of a low-dose benzodiazepine or anxiolytic are permitted and may be included in the study.

Cardiovascular disorders-related exclusion criteria:

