To maintain consistency of reporting across clinical sites, findings of ARIA-E or ARIA-H on MRI are determined by the MRI Central Reader by radiologists with expertise in assessing for ARIA and other abnormalities on brain MRI. ARIA-E, ARIA-H and other findings are documented on and reported to the sites with the BMW report (see Section 6.5.12). The BMW provided by the Central Reader after each MRI examination scores ARIA-E (parenchymal vasogenic edema, leptomeningeal/sulcal effusion) according to: extent, location, number of sites involved, radiographic severity (mild, mild+, moderate, moderate+, severe) (Table 6) and changes since prior MRI exams. ARIA-E findings typically resolve radiographically and will be noted as such on the BMW of follow-up MRI scans. The BMW also documents occurrence and characteristics (location, size, number) of ARIA-H (parenchymal microhemorrhages and leptomeningeal hemosiderosis and macrohemorrhages).

Overall, ARIA-H radiographic severity is defined as the worst individual radiographic severity for microhemorrhages, leptomeningeal hemosiderosis or macrohemorrhages (eg, if there are

Alector, Inc.

4 incident microhemorrhages, 1 incident areas of leptomeningeal hemosiderosis and no macrohemorrhages, then ARIA-H is rated as "Moderate") (Table 6).

Table 6: ARIA-E and ARIA-H Radiographic Severity Scales

ARIA-E Characterization:		Severity/Grade	
<5 cm monofocal		Mild (Grade 1)	
<5 cm multifocal		Mild+ (Grade 2)	
5-10 cm monofocal	N	Moderate (Grade 3)
5-10 cm multifocal	Moderate+ (Grade 4)		
>10 cm monofocal/multifocal	Severe (Grade 5)		
Incident ARIA-H:	Mild	Moderate	Severe
microhemorrhages	1-4	5-9	10 or more
Areas of leptomeningeal hemosiderosis	NA	1	2 or more
macrohemorrhages	NA	NA	1 or more

ARIA-E=amyloid-related imaging abnormalities-edema; ARIA-H=amyloid-related imaging abnormalities-hemosiderin deposits; NA=not applicable.

ARIA-H findings very rarely resolve radiographically; it is more typical for ARIA-H findings to stabilize radiographically. Radiographic stabilization of an ARIA-H finding is defined as when a follow-up MRI scan shows no increase in number/size/extent of previously seen cerebral microhemorrhages, leptomeningeal hemosiderosis and cerebral macrohemorrhages.

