## 7.5.7 Magnetic Resonance Imaging (MRI) for Detection of ARIA-E and ARIA-H

Incidence of the first occurrence of ARIA-E within each post-baseline visit will be summarized by radiographic severity for each visit (refer to Table 7-9 for analysis visit window definition) and overall during the treatment period. The same incidence table will be summarized for post-baseline new ARIA-H. In addition to radiographic severity for ARIA-H, individual radiographic severity for microhemorrhages, leptomeningeal hemosiderosis, and macrohemorrhages for the first occurrence of new ARIA-H will also be summarized by visit and overall during the treatment period.

Incidence of any occurrence of ARIA-E within each post-baseline visit will be summarized in the same fashion. In the case of multiple values in the baseline analysis visit window, the rules described in the Section 7.1.3.2 still apply. In the case of multiple values in a post-baseline analysis visit window, the

Protocol No. AL002-2 Last Revision Date: 12 Aug 2025

rules described in the Section 7.1.3.2 do not apply to this summary, but the worst-case scenario will be applied as below:

- A participant having a record indicating no ARIA-E and a different record indicating ARIA-E is considered experienced ARIA-E per visit or overall.
- A participant having experienced ARIA-E more than once per visit or overall is counted once in the number of participants with ARIA-E per visit or overall.
- The maximum severity is selected if ARIA-E was observed more than once for a participant per visit or overall post-baseline.

The same incidence table will be summarized for post-baseline new ARIA-H. In the case of multiple values in an analysis visit window, the same rules described above apply. In addition to radiographic severity for ARIA-H, individual radiographic severity for microhemorrhages, leptomeningeal hemosiderosis, and macrohemorrhages for the any occurrence of new ARIA-H will also be summarized by visit and overall during the treatment period. The maximum severity of ARIA-H is selected for a participant per visit or overall post-baseline, and the individual radiographic severity corresponding to the selected ARIA-H will be summarized per visit or overall post-baseline.

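### The by-visit any-occurrence table for new ARIA-H shows prevalence above baseline, not incidence, because each scan is compared with baseline only

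*SAP*

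**What the plan says.** **Definition.** SAP 6.3.7.2.1 makes the single scan the unit: "A new event of ARIA-H is defined as an MRI scan at a post-baseline visit if any of the criteria below" is satisfied. The first criterion is "CFB in the number of microhemorrhages > 0, or". The second has the same form for areas of leptomeningeal hemosiderosis (siderosis below). The third is "Presence of macrohemorrhages", with no reference to baseline. SAP Table 6-4 grades severity on the same change-from-baseline scale.

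**Tables.** SAP 7.5.7 plans a by-visit table of first occurrence of ARIA-E, and then a second one: "Incidence of any occurrence of ARIA-E within each post-baseline visit will be summarized in the same fashion". After each it adds the ARIA-H counterpart: "The same incidence table will be summarized for post-baseline new ARIA-H". Within a visit, and again overall, a participant is counted once. Time to first occurrence and a Kaplan-Meier curve are also planned for new ARIA-H.

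**Persistence.** Protocol 7.11 states: "ARIA-H findings very rarely resolve radiographically; it is more typical for ARIA-H findings to stabilize radiographically". It adds: "Radiographic stabilization of an ARIA-H finding is defined as when a follow-up MRI scan shows no increase in number/size/extent of previously seen cerebral" microhemorrhages, siderosis or macrohemorrhages.

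**Truncation.** Under SAP 7.1.1.2.2, safety data collected more than 90 days after the last dose are listed but left out of by-visit summaries.

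**The concern.** An unchanged follow-up scan is stable under protocol 7.11 and a new event under SAP 6.3.7.2.1. Protocol 7.11.1.2 requires unscheduled MRIs every 4 to 6 weeks until ARIA-H has stabilized, so even the scan that confirms stability meets the SAP's definition of a new event.

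The any-occurrence layout suits ARIA-E, which typically resolves. Carried over to ARIA-H, it puts persistent lesions into every later row.

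ARIA-H is an adverse event of special interest and a stated identified risk. Protocol Table 7 allows dosing to restart after mild or moderate asymptomatic ARIA-H has stabilized, so whether further lesions follow is a real safety question. A Week 48 or Week 96 row headed as incidence of new ARIA-H will be read as the answer, and an arm with more early ARIA-H will appear to have more late bleeding. ARIA-E has planned recurrence and resolution summaries. ARIA-H has only first occurrence.

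**Working it through.** **The plan's own example.** SAP 6.3.7.2.2 rates 4 incident microhemorrhages, 1 incident siderosis area and no macrohemorrhage as Moderate. From Table 6-4: 4 microhemorrhages is Mild, 1 siderosis area is Moderate, and the worst is Moderate. This agrees.

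**Scan schedule.** Protocol 7.11.1.1 places Part 2 scans 5 to 10 days before Doses 2, 3 and 4 and before Weeks 25, 49, 73 and 97: 3 + 4 = 7 over 96 weeks, and 3 + 2 = 5 through Week 49. With dosing on target days, the scans fall on Days 19–24, 47–52, 75–80, 159–164, 327–332, 495–500 and 663–668. Under SAP Table 7-9 the first falls in the Week 2 or Week 4 window, the second in Week 6 or Week 8, and the rest in Weeks 12, 24, 48, 72 and 96. Each scan therefore has its own row.

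**The two rules.** Let c0 be the baseline count and ct the count at scan t.
- SAP rule: new at t if ct − c0 > 0.
- Comparison with earlier scans: new at t if ct exceeds the highest of c0, …, c(t−1).

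Microhemorrhage counts for hypothetical participants on drug with every scheduled scan done and no unscheduled scans:

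| Baseline; later scans | Visits new, SAP rule | Visits new, earlier-scan rule | First per participant | Overall |
|---|---|---|---|---|
| 0; 1,1,1,1,1,1,1 | 7 of 7 | 1 of 7 | 1 | 1 |
| 0; 1,1,1,1,1 (48 weeks) | 5 of 5 | 1 of 5 | 1 | 1 |
| 0; 0,0,0,1,1,1,1 | 4 of 7 | 1 of 7 | 1 | 1 |
| 1; 1,1,1,1,1,1,1 | 0 of 7 | 0 of 7 | 0 | 0 |
| 0; 1,2,3,4,5,5,5 | 7 of 7 | 5 of 7 | 1 | 1 |

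The fourth line shows that a microhemorrhage present at baseline is never counted. In the last line severity is Mild at changes of 1 to 4 and Moderate from 5, so five successive new lesions appear as a single grade change.

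**Effect of the 90-day limit.** If the first scan led to permanent discontinuation, the last dose is Day 1 and summaries stop at Day 1 + 90 = Day 91. Only the scans on Days 19–24, 47–52 and 75–80 remain: 3 rows, not 7.

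**Proportions.** The documents give no ARIA-H rate, so the interval probabilities p of a new lesion below are assumptions, with lesions persistent and everyone scanned and on drug. The SAP row at visit t is 1 − ∏(1 − p) over the intervals up to t.

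| Assumed p over the 7 intervals (%) | SAP row, Weeks 24 / 48 / 72 / 96 (%) | Truly new (%) |
|---|---|---|
| 5, 5, 3, 0, 0, 0, 0 | 12.5 / 12.5 / 12.5 / 12.5 | 0 / 0 / 0 / 0 |
| half of that: 2.5, 2.5, 1.5, then 0 | 6.4 / 6.4 / 6.4 / 6.4 | 0 / 0 / 0 / 0 |
| 5, 5, 3, 2, 1, 1, 1 | 14.2 / 15.1 / 15.9 / 16.8 | 2 / 1 / 1 / 1 |
| 3, 3, 2, 2, 2, 2, 2 | 9.6 / 11.4 / 13.2 / 15.0 | 2 / 2 / 2 / 2 |

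First line: 1 − 0.95 × 0.95 × 0.97 = 0.125. Second line: 1 − 0.975 × 0.975 × 0.985 = 0.064. If those were two arms, the Week 96 rows would differ by 12.5 − 6.4 = 6.1 percentage points with no bleeding in either arm after the third scan.

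**The case against.** The strongest reply is that new means new since baseline. Table 6-4 openly equates incident with change from baseline, and the convention has a purpose. Protocol exclusion 14 reads "Participant has presence on MRI of >5 microbleeds and/or >1 area of leptomeningeal hemosiderosis based on central read", so participants may enter with up to 5 microbleeds, and the rule keeps those out. That stands as a reason to have the change-from-baseline definition. It does not make the by-visit rows incidence.

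Second, much of the section is unaffected. The overall row counts a participant once, and the first-occurrence table and Kaplan-Meier curve show when first bleeds happen in each arm. Severity by visit reveals bleeding that crosses a grade, and all MRI findings are listed. This stands. What is left is that no planned table shows further lesions after a participant's first event unless they change the grade. The first-occurrence table is safe only if read as first per participant; its wording, tied to each post-baseline visit, could also mean first within each window.

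Third, carry-over is limited. Protocol Table 7 permanently stops drug for severe ARIA-H and for symptomatic mild or moderate ARIA-H, and Part 1 participants with ARIA at Day 15 or Day 43 also stop. Their scans leave the by-visit summaries 90 days after the last dose. The common close also leaves fewer participants late: the sample-size section assumes 58% missing CDR-SB at month 24. This stands too. The cases that stay in the table are mainly asymptomatic mild or moderate ARIA-H with dosing restarted.

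Three stronger readings are tempting and are not supported:
- *The table would rise through Weeks 48 to 96 even if all bleeding were early.* It would stay flat; a rise needs continuing new cases, as in the third and fourth sets of assumed rates.
- *The overall ARIA-H rate is inflated, or one lesion adds seven events to a total.* The SAP counts participants and never sums events over scans.
- *Microhemorrhages or siderosis present at entry are counted as new.* Their change from baseline is zero. Only a macrohemorrhage counts on presence alone, and exclusion 2 names macro-hemorrhage among its examples of excluded disease.

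**Conclusion.** The point holds for the by-visit rows of the any-occurrence ARIA-H table in SAP 7.5.7, and for the first-occurrence table only if that is read as first within each window. Those rows report prevalence of ARIA-H above baseline, within 90 days of the last dose, under an incidence label. For one stable microhemorrhage from the first scan the count is 7 of 7 visits against 1 of 7, or 5 of 5 against 1 of 5 over 48 weeks. This assumes the participant stays on drug, is scanned as scheduled and the lesion persists unchanged. The mislabelling follows from the rule at any bleeding rate; the percentages above only illustrate it.

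No efficacy test, decision rule or overall ARIA-H incidence changes. It is still worth correcting: this is a safety event of special interest, the late rows could be taken for continuing bleeding or a late difference between arms, and no other planned table would put that right.

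**What to change.** 1. In SAP 7.5.7, relabel the by-visit any-occurrence ARIA-H rows as *prevalence of ARIA-H above baseline*, keeping the Table 6-4 severity grading.
2. In SAP 6.3.7.2.1, add a definition of ARIA-H new since earlier scans: a count above the highest on any earlier scan, baseline included, taken separately for microhemorrhages and siderosis areas; or a macrohemorrhage not seen on any earlier scan.
3. Add a by-visit row or table using that definition, with participants scanned in the window as the denominator. Show the Table 6-4 change-from-baseline severity at that scan, so no second grading scale is needed.
4. State that first occurrence means first per participant.

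The overall row, time to first occurrence and Kaplan-Meier outputs stay as planned. The cost is SAP wording, one derived flag and one extra table. The Brain MRI Worksheet already records the number and location of lesions, so nothing further has to be collected.
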